3.2 Secondary Objective(s) & Hypothesis(es)

- (1) **Objective:** To compare ORR and DCR per RECIST 1.1 as assessed by BICR in subjects treated with a combination of pembrolizumab plus axitinib versus sunitinib monotherapy. DOR will also be evaluated.

Hypothesis: The combination therapy of pembrolizumab plus axitinib is superior to sunitinib monotherapy with respect to ORR as assessed by BICR per RECIST 1.1.

- (2) **Objective:** To evaluate PFS rate per RECIST 1.1 as assessed by BICR at 12, 18, and 24 months based on data adequacy; to evaluate OS rates at 12, 18, and 24 months based on data adequacy.
- (3) **Objective:** To evaluate and compare safety and tolerability profiles in subjects treated with pembrolizumab plus axitinib versus sunitinib monotherapy.
- (4) **Objective:** To compare time to deterioration (TTD) based on the Functional Assessment of Cancer Therapy Kidney Symptom Index—Disease-Related Symptoms (FKSI-DRS) scale in subjects treated with pembrolizumab plus axitinib versus sunitinib monotherapy.
- (5) **Objective:** To assess the longitudinal score changes from baseline to 42 weeks as measured by European Organization for the Research and Treatment of Cancer (EORTC) QLQ-C30 global health status/quality of life scale.

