8.6.2 Statistical Methods for Safety Analyses

Safety and tolerability will be assessed by clinical review of all relevant parameters including AEs, laboratory tests, and vital signs.

Tiered Approach

The analysis of safety results will follow a tiered approach (Table 19). The tiers differ with respect to the analyses that will be performed. For this protocol, there are no Tier 1 events.

Tier 2 parameters will be assessed via point estimates with 95% CIs provided for between-group comparisons; only point estimates by treatment group are provided for Tier 3 safety parameters.

Adverse events (specific terms as well as system organ class terms) will be classified as belonging to "Tier 2" or "Tier 3", based on the number of events observed. Membership in Tier 2 requires that at least 10% of the subjects in any treatment group exhibit the event; all other AEs and predefined limits of change will belong to Tier 3.

The threshold of at least 10% of subjects with events was chosen for Tier 2 event because the incidence rate would allow meaningful statistical assessments; events reported in less frequent than 10% of subjects would obscure the assessment of overall safety profile and add little to the meaningful interpretation. Because many 95% CIs may be provided without adjustment for multiplicity, the confidence intervals should be regarded as a helpful descriptive measure to be used in review, not a formal method for assessing the statistical significance of the between-group differences in AEs and predefined limits of change.

Continuous measures such as changes from baseline in laboratory values and vital signs that are not pre-specified as Tier 1 safety parameters will be considered Tier 3 safety parameters. Summary statistics for baseline, on-treatment, and change from baseline values will be provided by treatment group in table format.

In addition, the broad clinical and laboratory AE categories consisting of the percentage of subjects with Grade 3-5 AE (incidence $\geq 5\%$ of subjects in one of the treatment groups) and any SAE (incidence $\geq 5\%$ of subjects in one of the treatment groups) will be considered Tier 2 endpoints.

The threshold of at least 5% of subjects with events was chosen for Tier 2 Grade 3-5 AEs and SAEs because the incidence rate would allow meaningful statistical assessments; those AEs are expected to happen less frequent than specific AEs/SOCs but important for overall safety profile assessment.

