The broad clinical and laboratory AE categories consisting of the percentage of subjects with any AE, any Grade 3-5 AE (incidence $< 5\%$ of subjects in one of the treatment groups), any SAE (incidence $< 5\%$ of subjects in one of the treatment groups), any drug-related AE, any AE that is both drug-related and Grade 3-5, any AE that is both serious and drug related, dose modification due to AE, discontinuation due to an AE, and death will be considered Tier 3 endpoints.

Note that 95% CIs will be provided for between- treatment differences in the percentage of subjects with Tier 2 events; these analyses will be performed using the Miettinen and Nurminen method, an unconditional, asymptotic method.

Table 19 Analysis Strategy for Safety Parameters

Safety Tier	Safety Endpoint	95% CI for Treatment Comparison	Descriptive Statistics
Tier 2	Any Serious AE (incidence $\geq 5\%$ of subjects in one of the treatment groups)	X	X
	Any Grade 3-5 AE (incidence $\geq 5\%$ of subjects in one of the treatment groups)	X	X
	Specific AEs or SOCs (incidence $\geq 10\%$ of subjects in one of the treatment groups)	X	X
Tier 3	Any AE		X
	Any Serious AE (incidence $< 5\%$ of subjects in one of the treatment groups)		X
	Any Grade 3-5 AE (incidence $< 5\%$ of subjects in one of the treatment groups)		X
	Any Serious and Drug-related AE		X
	Any Grade 3-5 and Drug-related AE		X
	Dose Modification due to AE		X
	Discontinuation due to AE		X
	Death		X
	Specific AEs or SOCs (incidence $< 10\%$ of subjects in all of the treatment groups) or PDLCs		X
	Change from Baseline Results (Labs, ECGs, Vital Signs)		X

Abbreviations: AE = adverse event; CI = confidence interval; ECG = electrocardiogram; PDLC = pre-defined limit of change; SOC = system organ class.

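### The 5% rules for SAEs and Grade 3-5 AEs put an event that straddles 5% in both safety tiers, and four tolerability outcomes are denied a between-arm CI whatever their incidence

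*Combined protocol and SAP*

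**What the plan says.** Secondary objective 3 (Section 3.2) is comparative: "To evaluate and compare safety and tolerability profiles in subjects treated with pembrolizumab plus axitinib versus sunitinib monotherapy". Section 8.6.2 and Table 19 set out how that comparison is reported.

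- **What each tier receives.** For Tier 2, "95% CIs will be provided for between- treatment differences in the percentage of subjects with Tier 2 events", by the Miettinen and Nurminen method. For Tier 3, "only point estimates by treatment group are provided for Tier 3 safety parameters".
- **The 5% rule, Tier 2.** The text ends "any SAE (incidence $\geq 5\%$ of subjects in one of the treatment groups) will be considered Tier 2 endpoints"; Grade 3-5 AEs have the same rule.
- **The 5% rule, Tier 3.** SAEs and Grade 3-5 AEs below 5% are also defined by one arm. The wording after the 5% figure is "of subjects in one of the treatment groups), any drug-related AE". Table 19 repeats it.
- **The 10% rule for specific AE terms and SOCs.** Here the Tier 3 row of Table 19 reads "of subjects in all of the treatment groups) or PDLCs", the proper complement of 10% or more in one arm.
- **Outcomes assigned to Tier 3 with no threshold.** These include "any AE that is both drug-related and Grade 3-5, any AE that is both serious and drug related", followed by "dose modification due to AE, discontinuation due to an AE, and death will be considered Tier 3 endpoints". Their rows in Table 19 have no mark in the CI column.

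The stated reason for both cut-offs is that incidence at that level permits a meaningful statistical assessment. The section also says the intervals are unadjusted and descriptive.

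**The concern.** There are two separate faults.

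First, the 5% rules are not complementary. The events that fall in both tiers are those at or above 5% in one arm and below it in the other, which include clear imbalances between arms. Whether such an event gets an interval would be settled after the data are seen, in an open-label trial.

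Second, a single AE term at 10% in one arm gets a difference and CI, whereas stopping treatment for an AE at 15% cannot. Discontinuation and dose modification bear directly on whether the combination is harder to tolerate than sunitinib. The plan's incidence rationale does not explain leaving them out, because they are excluded by name and not by frequency.

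**Working it through.** The plan states no figure that depends on the tier rules, so there is none to reproduce. Two checks apply.

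**1. Apply the written 5% rules to example incidences.**

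Tier 2 if max(a, b) ≥ 5%. Tier 3 as written if min(a, b) < 5%. Tier 3 as proposed if max(a, b) < 5%.

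| Arm 1 vs arm 2 | Tier 2 | Tier 3 as written | Tier 3 if all arms < 5% |
|---|---|---|---|
| 8% vs 3% | yes | yes | no |
| 6% vs 4% | yes | yes | no |
| 6% vs 7% | yes | no | no |
| 3% vs 4% | no | yes | yes |

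Every pair that straddles 5% is in both tiers as written. With the proposed rule each pair falls in exactly one.

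**2. Ask whether the excluded outcomes are too rare for a CI, and what a CI would show.**

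Inputs from the documents:
- Phase 1b discontinuation for AEs (Section 4.2.1): pembrolizumab 7/52 = 13.5%, axitinib 8/52 = 15.4%. Each is a rate for one drug of the pair. Both exceed 5% and 10%.
- Randomized N = 861, 1:1 (Section 8.9): 861/2 = 430.5. I use 430 per arm. The as-treated population can only be the same size or smaller.

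Assumptions: 64 combination events (64/430 = 14.9%, close to the phase 1b axitinib rate) and various sunitinib counts. The documents give no sunitinib rate.

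The Miettinen-Nurminen limits are the two values of δ that solve

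(p1 − p2 − δ)² = 1.96² × [p̃1(1 − p̃1)/n1 + p̃2(1 − p̃2)/n2] × N/(N − 1),

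where p̃1 and p̃2 are the maximum-likelihood rates under p̃1 − p̃2 = δ, n1 = n2 = 430 and N = 860.

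| Events, combination vs sunitinib | Difference (points) | 95% CI |
|---|---|---|
| 64 vs 64 (14.9% vs 14.9%) | 0.0 | -4.8 to 4.8 |
| 64 vs 43 (14.9% vs 10.0%) | 4.9 | 0.5 to 9.4 |
| 64 vs 45 (14.9% vs 10.5%) | 4.4 | -0.03 to 8.9 |
| 58 vs 43 (13.5% vs 10.0%) | 3.5 | -0.8 to 7.9 |
| 34 vs 13 (7.9% vs 3.0%), an SAE that straddles 5% | 4.9 | 1.9 to 8.1 |

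The half-width for discontinuation is about 4.5 points (for 64 vs 43, (9.4 − 0.5)/2 = 4.45), which is narrow enough to be informative. Whether the interval excludes zero turns on two sunitinib events, so no row predicts the result. The last row shows a clear difference for which the written rule does not settle whether an interval is reported.

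**The case against.** The other side has several good points.

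- **The main overall safety rates are covered.** Any SAE and any Grade 3-5 AE get a CI at 5% or more in one arm. Grade 3-4 AEs were 30/52 = 57.7% in phase 1b, so that CI would be shown. A reader might infer that the plan gives no interval for overall tolerability; it does not go that far. This stands and narrows the point to four outcomes.
- **Death is compared elsewhere.** OS is a primary endpoint with a stratified log-rank test, hazard ratio and 95% CI (Section 8.6.1.2). A crude difference in as-treated death percentages ignores follow-up time and adds little. This stands.
- **Threshold clearance is documented only for AE discontinuation.** The documents give no rates for dose modification, drug-related SAEs or drug-related Grade 3-5 AEs. A reader might infer that all of them exceed the cut-offs, but that is not shown. The complaint is that they are excluded whatever their rate.
- **The rows are hard to compare across arms.** A combination subject may stop one drug and continue the other. Dose reduction applies only to axitinib and sunitinib, and sunitinib has a scheduled break. Without a definition a CI would mean little. This stands and changes the fix. Drug-relatedness is also judged by investigators who know the treatment, and an interval does not measure that bias.
- **The overlap is a slip.** The 10% row shows what was meant. If the 5% rule covers only the overall any-SAE and any-Grade 3-5 rates, straddling 5% is implausible. But the rationale for the 8.6.2 change in the Summary of Changes speaks of events reported in under 5% of subjects, which suggests the rule sorts individual events. The text should say which.
- **Readers could compute a crude interval from the per-arm percentages.** True, but that is no reason to leave it out of a prespecified comparison.

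**Conclusion.** Both parts hold, as reporting faults in the safety analysis. The overlap follows from the wording alone and needs no assumption about rates; its reach depends on whether the 5% rule is applied to individual events or only to the overall categories. The second part covers four outcomes: discontinuation due to AE, dose modification due to AE, drug-related Grade 3-5 AE and drug-related SAE. The evidence that the exclusion is not a matter of rarity is firm for discontinuation only, and rests on single-drug rates from 52 subjects.

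A reader might take 64 versus 43 events to mean that the plan would hide a significant excess of discontinuations. The documents do not support that: the sunitinib count is assumed, and at 45 events the interval includes zero. What is lost is about ±4.5 points of stated precision on a comparison that the objectives call for. Type I error, power, interim boundaries and efficacy conclusions are unaffected. The change should be made, but the trial's main conclusions do not depend on it.

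**What to change.** In Section 8.6.2 and Table 19:

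1. For SAEs and Grade 3-5 AEs, change the Tier 3 condition to *less than 5% of subjects in all of the treatment groups*, in both text and table. State whether the rule applies to individual event terms, to the overall category, or to both.
2. Report the Miettinen-Nurminen difference and 95% CI, still labelled descriptive and unadjusted, for discontinuation due to AE, dose modification due to AE, drug-related Grade 3-5 AE and drug-related SAE.
3. Before doing so, state for the combination arm whether discontinuation and dose modification count action on any component or on all components. If both versions are wanted, report each.
4. Leave death in Tier 3, with a cross-reference to the OS analysis.
5. In the same edit, reconcile the overall drug-related AE category, which is in the Tier 3 text but appears to have no row in Table 19.

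The cost is one phrase, one definition and at least four more intervals per report, with no extra subjects or follow-up. The downside is a few more unadjusted intervals, which the section already tells readers to treat as descriptive.

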Study treatments will continue until progressive disease (PD) is BICR-verified or further confirmed by the investigator, unacceptable adverse events (AEs) or intercurrent illness prevents further administration of treatment, death or withdrawal of consent. When a subject is first identified with PD by the investigator, the site will request PD to be verified by BICR. Subjects who are clinically stable may continue treatment while waiting for BICR verification. Progressive disease status may be further confirmed by subsequent scans at the site. Detailed descriptions of imaging-based disease assessments, PD verification by BICR, and PD confirmation at the site are provided in Section 7.1.2.7.2 and Section 7.1.2.7.6.

For the combination arm, pembrolizumab will be administered for a maximum of 35 doses. If a subject remains progression-free after 35 doses of pembrolizumab, treatment with axitinib will be continued as monotherapy until PD is verified by BICR or further confirmed by the investigator. In addition, if 1 of the 2 compounds needs to be discontinued because of toxicity or intolerance, treatment with the other compound as monotherapy will be continued until PD is verified by BICR or further confirmed by the investigator. For both arms, in the event that a complete response (CR) has been observed in a subject, study treatment may be discontinued at the discretion of the investigator after the CR has been confirmed and after a minimum of 8 cycles of treatment (~24 weeks) in the pembrolizumab plus axitinib arm or 4 cycles of treatment (~24 weeks) in the sunitinib arm have been received. Detailed criteria for study treatment discontinuation and re-treatment are described in Section 5.8.

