All adverse events that occur after the consent form is signed but before treatment allocation/randomization must be reported by the investigator if they cause the subject to be excluded from the trial, or are the result of a protocol-specified intervention, including but not limited to washout or discontinuation of usual therapy, diet, placebo treatment or a procedure. From the time of treatment allocation/randomization through 30 days following cessation of treatment, all adverse events must be reported by the investigator. Such events will be recorded at each examination on the Adverse Event case report forms/worksheets. The reporting timeframe for adverse events meeting any serious criteria is described in section 7.2.3.1. The investigator will make every attempt to follow all subjects with non-serious adverse events for outcome.

Electronic reporting procedures can be found in the Electronic Data Capture (EDC) data entry guidelines. Paper reporting procedures can be found in the Investigator Trial File Binder (or equivalent).

7.2.1 Definition of an Overdose for This Protocol and Reporting of Overdose to the Sponsor

In this trial, an overdose is any dose exceeding 5 times the prescribed dose of pembrolizumab (200 mg), defined as any dose higher than 1000 mg. No specific information is available on the treatment of overdose of pembrolizumab. In the event of overdose, pembrolizumab should be discontinued and the subject should be observed closely for signs of toxicity. Appropriate supportive treatment should be provided if clinically indicated. Overdose for sunitinib and axitinib is any dose exceeding the prescribed maximum dose for each drug (i.e., 5 mg BID for axitinib unless dose escalation to 7 mg or 10 mg BID is permitted per Section 5.2.1.2.1. or 50 mg QD for sunitinib). There is no specific treatment for sunitinib or axitinib overdose. In the event of overdose, the dose should be interrupted and the subject should be observed closely for signs of toxicity. Appropriate supportive treatment should be provided if clinically indicated. The subject may resume study treatment at the discretion of the investigator (refer to axitinib and sunitinib labeling for more details).

If an adverse event(s) is associated with ("results from") the overdose of Sponsor's product or vaccine, the adverse event(s) is reported as a serious adverse event, even if no other seriousness criteria are met.

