8.9 Sample Size and Power Calculations

The study will randomize subjects in a 1:1 ratio into the experimental arm of pembrolizumab+axitinib and the control arm of sunitinib. Both PFS and OS are primary endpoints for this study. The sample size was planned for 840 but the following power calculations are based on the actual final number of randomized subjects (N = 861).

For the PFS endpoint, based on a target number of 487 PFS events and one interim analysis at approximately 75% of the target number of events, the study has ~99% power to detect an HR of 0.60 (pembrolizumab+axitinib combination versus sunitinib) at $\alpha=0.2\%$ (1-sided). The calculation assumes an HSD α -spending function with $\gamma=-2$ to control the overall Type I error rate for this endpoint at 0.2% (1-sided). The target numbers of PFS events for the first interim and final analysis are projected to occur at 22 and 31 months respectively.

For the OS endpoint, based on a target number of 404 final OS events and 2 interim analyses (with approximately 48% of final OS events at IA1 and 74% of the final OS events at IA2), the

study has approximately 80% power to detect an HR of 0.75 at an overall alpha level of 2.3% (1-sided). The calculation assumes that a linear α -spending function with a fixed α -spending of 0.0001 at IA1 and the rest α -spending approximated by an HSD α -spending function with $\gamma=-4$ to control the overall Type I error rate for this endpoint at 2.3% (1-sided). The target number of OS events is projected to occur at 43 months after the start of the study. The target numbers of OS events for the first and second interim analyses are projected to occur at 22 months and 31 months respectively.

The above calculations assume an exponential distribution with a median of 13 months for PFS and a median of 33 months for OS for the control group respectively, a yearly dropout rate of 10% for PFS and 1% for OS, and an enrollment of 15 months, with monthly accrual of 40 to 60 patients in the first 3 months and monthly accrual of ~60 patients after the first 3 months. The median PFS and median OS assumptions in the control group are based on emerging data of sunitinib from the CheckMate 214 study (59).

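### Section 8.6.2 compares adverse events between arms only as crude percentages, so for events that keep accruing on treatment the arm with slower progression shows an excess even when event rates are equal

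*Combined protocol and SAP*

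**What the plan says.** Comparing safety and tolerability between the arms is a secondary objective (Section 3.2, objective 3). The method is in Section 8.6.2: "95% CIs will be provided for between- treatment differences in the percentage of subjects with Tier 2 events", by the Miettinen and Nurminen method. Entry to the compared set also rests on a crude percentage: "Membership in Tier 2 requires that at least 10% of the subjects in any treatment group exhibit the event", with a 5% threshold for serious and Grade 3-5 events. The section says that "the confidence intervals should be regarded as a helpful descriptive measure to be used in review"; the reason it gives is the number of intervals without multiplicity adjustment, not unequal exposure.

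The time over which events can be counted depends on progression. Section 2.1: "Study treatments will continue until progressive disease (PD) is BICR-verified or further confirmed by the investigator". After the cap of 35 pembrolizumab doses, "treatment with axitinib will be continued as monotherapy until PD is verified by BICR". If one drug of the pair is stopped for toxicity, "treatment with the other compound as monotherapy will be continued until PD is verified by BICR or further confirmed by the investigator". Section 7.2: "From the time of treatment allocation/randomization through 30 days following cessation of treatment, all adverse events must be reported by the investigator".

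For PFS, Section 8.9 says "the study has ~99% power to detect an HR of 0.60", with exponential times, a control median of 13 months, 10% yearly dropout and 15 months of enrolment.

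Section 8 contains no person-time rate, fixed-window incidence or time-to-first-event comparison for AEs. Section 8.12 summarises exposure in cycles. Under Section 5.2.3 a cycle is 21 days in the combination arm and 42 days in the sunitinib arm.

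**The concern.** The percentage of subjects who ever have an event rises with the time they are watched. Here that time ends 30 days after treatment stops, and treatment stops mainly at progression. If the combination delays progression as the plan assumes, its subjects are watched for longer, and events that arise steadily on treatment reach a higher percentage even at the same monthly risk. The better the combination works, the larger this part of the difference becomes.

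The percentage difference then mixes two things: how toxic the regimen is per unit of time, and how long subjects stay on it. The planned tables give a reader no way to separate them. The exposure table does not help directly, because its unit is twice as long in one arm as in the other.

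**Working it through.** **1. The plan's own PFS figures.** Power with 487 events, HR 0.60 and one-sided alpha 0.2%: Φ(√(487/4) × |ln 0.60| − 2.878) = Φ(11.03 × 0.511 − 2.878) = Φ(2.76) = 99.7%. With the Table 20 bounds (3.06 and 3.00 at 365 and 487 events) it is 99.6%. The plan states about 99%. With Section 8.9's medians, dropout and accrual, the expected PFS events are 358 at 22 months (plan: 365) and 485 at 31 months (plan: 487). The plan's progression model is therefore reproduced closely.

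**2. Inputs for time at risk.**
- Progression hazard per month: sunitinib ln 2/13 = 0.0533; combination 0.60 × 0.0533 = 0.0320 (median 13/0.60 = 21.7 months).
- Dropout hazard: −ln(0.90)/12 = 0.0088, used in one set of runs and set to zero in the other. k is the progression hazard plus the dropout hazard.
- Cutoffs T = 22, 31 and 43 months (Section 8.1).
- Assumptions not in the documents: uniform entry over the 15 months, treatment ending only at progression or dropout, a full tail a = 30 days = 0.99 months, and the same constant AE hazard h in both arms.

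**3. Mean time at risk.** Averaging min(time to stop + a, time to cutoff) over entry gives

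a + 1/k − [e^(−k(T−15−a)) − e^(−k(T−a))] / (15k²).

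At T = 31 without dropout:
- sunitinib: 0.99 + 18.76 − (0.449 − 0.202)/0.0426 = 13.9 months;
- combination: 0.99 + 31.26 − (0.619 − 0.383)/0.01535 = 16.9 months.

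**4. Crude percentage with an event.** For a subject with time L to cutoff, the probability is

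1 − { k/(k+h) × e^(−ha) × [1 − e^(−(k+h)(L−a))] + e^(−k(L−a) − hL) },

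averaged over entry. Each cell gives sunitinib vs combination; differences were taken before rounding.

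| Cutoff | Dropout | Mean months at risk (ratio) | h = 0.02/month | h = 0.05/month | h = 0.10/month |
|---|---|---|---|---|---|
| 22 | none | 10.4 vs 11.8 (1.13) | 18.3 vs 20.5% (+2.3) | 38.3 vs 42.5% (+4.2) | 59.3 vs 64.5% (+5.2) |
| 22 | 10%/yr | 9.9 vs 11.2 (1.13) | 17.5 vs 19.5% (+2.1) | 36.8 vs 40.7% (+3.9) | 57.4 vs 62.3% (+4.9) |
| 31 | none | 13.9 vs 16.9 (1.21) | 23.3 vs 27.7% (+4.4) | 45.9 vs 53.1% (+7.2) | 66.2 vs 73.9% (+7.7) |
| 31 | 10%/yr | 13.0 vs 15.6 (1.20) | 21.8 vs 25.7% (+3.9) | 43.4 vs 49.9% (+6.5) | 63.4 vs 70.5% (+7.1) |
| 43 | none | 16.7 vs 21.8 (1.31) | 26.5 vs 33.2% (+6.8) | 49.4 vs 59.2% (+9.8) | 68.1 vs 77.2% (+9.1) |
| 43 | 10%/yr | 15.1 vs 19.4 (1.28) | 24.3 vs 30.1% (+5.8) | 46.3 vs 54.8% (+8.5) | 65.0 vs 73.2% (+8.1) |

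The true difference in event rate is zero in every cell.

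**5. Early-onset events.** If all the risk falls in the first 3 months, the crude percentage is

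1 − e^(−ha) + e^(−ha) × h/(h+k) × [1 − e^(−(h+k)(3−a))].

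With dropout and h = 0.231, 0.119 and 0.035 this gives 48.4 vs 48.9%, 28.9 vs 29.3% and 9.6 vs 9.7%: an excess of half a point or less. Without the 30-day tail it is 0.3 to 1.4 points for sunitinib percentages of 10 to 50%.

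**6. The person-time rate in the early-onset case.** Numbers of events are almost equal, but the combination accumulates more event-free time. The first-event rate ratio, combination to sunitinib, is then about 0.9, 0.85 and 0.8 at 22, 31 and 43 months. The rate errs in the opposite direction.

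**The case against.** Several points on the other side stand.

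- **The crude percentage is a legitimate quantity.** It answers how many subjects ever had the event over their assigned treatment course. A reader might infer that the planned interval is centred on the wrong value. It is not; it estimates something other than toxicity per unit of time.
- **The intervals are descriptive.** There are no Tier 1 events and no safety hypothesis. A reader might convert the excess into a false positive test. With an assumed 430 per arm and 10% dropout, the expected differences at 31 months correspond to z of about 1.3, 1.9 and 2.2, and none at 22 months exceeds about 1.6. The plan disclaims that use, so this is a matter of interpretation and not of error control.
- **Equal toxicity does not always show as an excess.** Step 5 shows almost none for early-onset events, and the documents do not say which AEs keep accruing.
- **The ratio of medians overstates the gap.** The medians differ by a factor of 1.67, but the data cutoffs reduce the ratio of mean time at risk to about 1.13 to 1.31.
- **Toxicity stops could move the gap either way.** In the 52-subject Phase 1b study (Section 4.2.1), 13.5% stopped pembrolizumab and 15.4% stopped axitinib for AEs. No matching sunitinib rate is given, so a claim that monotherapy continuation widens the gap further cannot be sized.
- **Serious events have a longer tail.** Section 7.2.3.1 collects them for up to 90 days. With that tail and dropout, the excess at 31 months falls to 3.4, 5.4 and 5.5 points.

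Two replies carry less weight. Section 4.2.3.2 names time to onset as a safety parameter and Section 8.4.2 refers to it, but Section 8.6.2 gives it no between-arm method. A supplemental SAP might add one, but Section 8.6.2 does not say so.

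**Conclusion.** The point holds in a limited form. For events that keep accruing on treatment, the only planned between-arm AE comparison would show about 2 to 5 points more for the combination at 22 months, 4 to 8 at 31 and 6 to 10 at 43, with no difference in AE hazard. Mean time at risk is about 13%, 20 to 21% and 28 to 31% longer at those cutoffs. These figures rest on the plan's PFS assumptions, AE hazards of 0.02 to 0.10 per month that are constant and equal in both arms, a 30-day tail, and treatment ending only at progression or dropout. They are negligible for early-onset events, and unequal toxicity stops could change them.

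The documents do not support the broader reading that the planned analysis is invalid or that any excess for the combination would be spurious. The gap is that a descriptive percentage stands alone for an objective that asks for a comparison. It should be filled, but it does not threaten the confirmatory results.

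**What to change.** In Section 8.6.2 and Table 19, keep the crude percentages and add for Tier 2 events:

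1. As the lead addition, the cumulative incidence of first events by a fixed time common to both arms (for example Week 24), with a 95% CI for the difference. This holds up under both the steady and the early-onset pattern.
2. Exposure-adjusted first-event rates per person-month. Define time at risk as calendar time in the AE collection window, including the sunitinib off-weeks. Add a note that this rate can favour the longer-treated arm for early-onset events, so it is read together with item 1.

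In Section 8.12, report exposure in months.

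The cost is one extra set of descriptive tables from data already collected. No hypothesis, alpha allocation or study procedure changes.
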